## **7.5 Follow-up for Adverse Events**

A study team member will provide referrals, as appropriate, for treatment needs resulting from any adverse events or unanticipated problems. In the event of any medical concerns that arise, the research staff will contact the on-call GI physician at HDVCH.

## **7.6 Safety Monitoring**

The team will also report any significant study-related or unanticipated adverse events to the Institutional Review Board and to the study sponsor based upon institutional and sponsor guidelines. In addition, there are three Independent Monitoring Committee (IMC) members with expertise in radiology, psychiatry, and biostatistics who will assess the safety and study-related concerns. Two IMC members have expertise in pediatric research. Specifically, the member with expertise in biostatistics has a program of research pertaining to the assessment and psychological treatment of depression in Hispanic adolescents ([name]). The member with expertise in psychiatry ([name]) has a program of research on the identification of risk factors and outcomes in children and adolescents with chronic health conditions including HIV. Given that this study investigates the intersect of

pediatric chronic health conditions and mental health functioning, this experience and expertise is highly complementary. In addition, our radiologist member is well suited to assess MRI related issues/concerns. Any reportable events that occur (which includes the occurrence of any safety issues related to the scanning procedures or to a breakdown of confidentiality) will be reported to the IRB immediately. We will also regularly communicate with NCCIH regarding safety monitoring practices.

## 8. INTERVENTION DISCONTINUATION

- **Criteria for discontinuing intervention:** A participant will be considered discontinued if they explicitly state that they would like to withdraw from the research study and cease participation in the intervention or if study staff is unable to contact the child or their guardian after 2 weeks.
- **Possible reasons for discontinuation:** Based on prior research, common reasons for discontinuing the ADAPT intervention include scheduling difficulties and the participants' lack of proximity to the medical center. It will be continually reinforced throughout the intervention that participation is optional. Families will be informed if new treatments become available. The intervention will be discontinued if a participant experiences an increase in distress and pain symptoms throughout the intervention, or if the interventionist ([name]) determines that a participant's presentation warrants more targeted care outside of what the intervention offers. Given [name] expertise in pediatric pain psychology, she is well-suited to provide clinical oversight to make this determination. The intervention will be discontinued for all participants in the event of a study closure by the institute.
- Participation will be discontinued at any time at participant or parent request. Participants will continue to be followed with their permission if study intervention is discontinued. Should a randomized participant prematurely discontinue participation in the study, study measures and endpoints will continue to be collected if possible. Of note, based on prior research, if a participant discontinues the behavioral intervention it is unlikely that they will be retained for subsequent assessment visits. However, every effort will be made to collect endpoint and study measure data.

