### 6.2.5 Completion/Final Evaluation

A post assessment (including fMRI) will be completed for all participants approximately one week after completion of treatment or waitlist. Participants will complete the same assessment measures and procedures as administered at the baseline assessment in addition to measures that were administered at screening. Upon completion of this visit, participants will receive a \$100 gift card (Amazon; described in further detail in 6.2.2. *Enrollment, Baseline, and Randomization*).

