## **9.6 Data Analyses**

For fMRI analysis, image processing and data analysis will be accomplished by FSL software. Each subject's functional images will be registered to their structural data using a six-parameter linear 3D transformation and then nonlinearly warped to standard space (MNI152). Analyses of both BOLD and ASL data will be accomplished via mixed effects ANOVAs. Data will be coded prior to analysis to conceal patient status to ensure blinding.

Clusters of activation will be identified using a threshold of  $Z > 3.1$  and statistical significance will be estimated according to Gaussian random field theory. Functional connectivity analysis will be conducted (Aim 1) to identify changes in functional connectivity between the AMY-PFC in ADAPT completers vs. those in the waitlist condition. A seed to whole brain analytic approach will be used to identify any/all differences observed. Pain-related brain activations are expected to diminish for those that complete ADAPT compared to the waitlist condition (Aim 2). For the exploratory aim, mechanisms associated with a positive treatment response (decreased pain intensity/ unpleasantness/ anxiety during WL-SPT) after ADAPT will be identified. Normalization of abnormal connectivity patterns are predicted to categorize changes in pain and anxiety. Specifically, decreases in brain activations and reductions in functional connectivity will be examined in relation to improvements in pain and anxiety post treatment using multiple (linear) regression.

While all efforts will be made to minimize missing data through the use of electronic data capture and real-time adherence data collection, missing data is still inevitable in RCTs. Thus, we will employ several strategies to handle missing data with specific attention on how to handle missing not-at-random. Specifically,

missing data will be handled via ML estimation with auxiliary correlate inclusion (e.g., Graham, 2003; Enders, 2010). Missing not at random will be addressed with mixture MNAR methods (e.g., Gottfredson, Bauer, & Baldwin, 2014; Muthen, et al., 2011; Sterba & Gottfredson, 2015).

Given that other factors such as pubertal status and subjective pain levels could influence the outcome, these factors will be included in the analysis as control covariates. Each participant's exact age will be recorded at assessment allowing personnel to control for age as an additional covariate should the need become apparent during preliminary analyses.

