## **10. DATA COLLECTION AND QUALITY ASSURANCE**

### **10.1 Data Collection Forms**

Standardized, validated measures used in prior pediatric pain studies will be used (*6.1 Schedule of Evaluations*). These measures will be administered using the REDCap platform. Participants and caregivers will be given the option to either complete baseline and post-assessment measures during their respective baseline/post assessment visit or before this visit using their own electronic device (to reduce the length of the in-person visit). A blinded post-baccalaureate research coordinator will serve as the outcome assessor and collect data at assessment visits. Home practice during ADAPT will also be measured (online module completion). Should a randomized participant prematurely discontinue participation in the study, study measures and endpoints will continue to be collected if possible. Any concomitant interventions (i.e., medical and psychological) experienced by the participants (either allowed or prohibited) will also be assessed for and recorded at baseline and post assessments. Participants will provide the reason and duration of concomitant interventions at the baseline and post assessment visits.

To ensure confidentiality, identification numbers will be used on data collection forms in lieu of names. Regarding the use of online measures and web modules, material development will be conducted in accordance with MSU policies. Hardware for this study will be provided and maintained by MSU Informatics, which maintains a secure server for supporting projects that potentially contain protected health information (PHI) and are subsequently subject to compliance with federal and state regulations regarding data of this type. The data obtained from the web program will be stored on the server, which will be backed up regularly.

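### Section 9.6 states the Aim 1 comparison as ADAPT completers against the waitlist, although the rules that stop treatment for worsening can act only in ADAPT before the post scan and no scan date is set for a child stopped early

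*Combined protocol and SAP*

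**What the plan says.** **Stopping treatment.** Section 8 states: "The intervention will be discontinued if a participant experiences an increase in distress and pain symptoms throughout the intervention". Treatment also stops if the interventionist judges that the child needs other, more targeted care. A child counts as discontinued on asking to withdraw, or "if study staff is unable to contact the child or their guardian after 2 weeks".

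**After stopping.** Section 8 promises follow-up with permission and that "every effort will be made to collect endpoint and study measure data". Section 10.1 adds, for a randomized child who leaves the study early, that "study measures and endpoints will continue to be collected if possible". Section 8 also warns, from prior research, that "if a participant discontinues the behavioral intervention it is unlikely that they will be retained for subsequent assessment visits".

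**Scan date.** Section 6.2.5 says the post assessment "will be completed for all participants approximately one week after completion of treatment or waitlist". The Précis puts it about 6 weeks after randomization. Section 3 also mentions six weeks, probably meaning the length of the treatment or waiting period.

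**Who is analysed.** Section 9.3 defines a modified intent-to-treat population: children who complete an assessment after randomization. Section 9.6 says the Aim 1 analysis will identify "changes in functional connectivity between the AMY-PFC in ADAPT completers vs. those in the waitlist condition". For Aim 2 it predicts lower activation in children who complete ADAPT than in the waitlist. It names maximum likelihood (ML) with auxiliary variables and mixture missing-not-at-random (MNAR) methods for missing data.

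**The concern.** The waitlist has no treatment to stop before its post scan, since ADAPT is offered only afterwards (section 3). The two clinical stopping rules can therefore select children, on how they are doing, in one arm only. If Aim 1 is run as 9.6 words it, a subset of ADAPT chosen after randomization is compared with an unselected waitlist, on the primary endpoint.

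A child stopped for worsening can drop out of that comparison in two ways. The child may never be scanned, because 6.2.5 counts from a completion that this child does not reach. Or the child may be scanned and then left out as a non-completer. Home questionnaires alone might satisfy 9.3, but they supply no data for Aims 1 and 2. What is at stake is the protection that randomization gives to a comparison of about 20 usable scans per arm.

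**Working it through.** **1. The same child under each section.** Take a child whose ADAPT is stopped at week 4 for rising distress and pain.

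| Section | Consequence |
|---|---|
| 8 and 10.1 | Endpoints to be collected if possible |
| 6.2.5 | Covered by the words for all participants, but the date counts from completion |
| Précis | About 6 weeks after randomization; no rule applies this to early stoppers |
| 9.3 | Included if assessed |
| 9.6, Aim 1 | Not a completer, so excluded on the wording |

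Sections 9.3 and 9.6 disagree, and the plan does not say which governs.

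**2. Which date fits the plan.** In weeks after assignment, using section 3 and 6.2.5:
- Nominal: 1 (to start) + 6 + 1 = 8.
- End of nominal ADAPT: 1 + 6 = 7.
- Latest permitted for ADAPT: 3 + 8 + 1 = 12.
- Screening to post scan: 1 + 1 + 1 + 6 + 1 = 10, which matches the stated stay of about 10 weeks. The Précis date would give 8.

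The mixed date wording affects both arms and does not itself cause loss in ADAPT.

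**3. The plan's own loss figures (section 4).** 50 × 0.90 = 45, so 5 children are lost. 45 × 0.90 = 40.5, stated as 40 usable. No split by arm is given.

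**4. Illustration of size.** Assumptions: 25 per arm; rho is the correlation of worsening with the imaging endpoint, taken as 0.3 to 0.7; the 0.4 effect in 9.2 is read as SD units. If the worst k of 25 are lost, the retained mean shifts by rho × φ(z)/(1 − p), where p = k/25 and z is the (1 − p) normal quantile. At rho = 1 this gives 0.1616 for k = 2, 0.2273 for k = 3 and 0.350 for k = 5. The type I error for a shift b is Φ(b/SE − 1.96) + Φ(−b/SE − 1.96), with SE = √(1/22 + 1/23) = 0.298 for the 3/2 split and √(1/20 + 1/25) = 0.300 for the 5/0 split.

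| Losses | Shift at rho = 1 | Shift, rho 0.3–0.7 | Share of 0.4 | Type I error |
|---|---|---|---|---|
| All logistical, or rho = 0 | 0 | 0 | 0 | 5.0% |
| 3 ADAPT / 2 waitlist, the worst in each | 0.2273 − 0.1616 = 0.066 | 0.02–0.05 | 5–12% | 5.1–5.3% |
| 2 ADAPT for worsening, other 3 logistical | 0.162 | 0.05–0.11 | 12–28% | 5.3–6.7% |
| All 5 the worst ADAPT children | 0.350 | 0.10–0.25 | 26–61% | 6.4–12.9% |

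The formula slightly overstates the shift in small samples. In a simulation with n = 25, the k = 5 value is 0.336. With that value and 18 and 22 usable scans after movement loss, the top of the last row falls from 12.9% to about 11.5%. At rho = 0.1 the last three rows give 0.01, 0.02 and about 0.035 SD.

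By symmetry, two waitlist children lost for worsening and none in ADAPT would give the same 0.05 to 0.11 SD in the other direction. The type I figures are for one summary measure and do not carry over to whole-brain cluster inference at Z > 3.1.

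**The case against.** The other side has a good deal of substance.

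- **Stopped children will not be scanned.** A reader might infer this from section 8. The remark on retention is general, the usual reasons it gives for stopping are scheduling and distance, and it stands beside the promise of every effort. Nothing reports retention for children stopped because they worsened.
- **The result is biased in favour of ADAPT.** This is also tempting, but the documents do not show it. Withdrawal and loss of contact are open to both arms, and a waitlist child who worsens may leave too. That connectivity follows symptoms over weeks is an assumption. The exploratory aim concerns ratings during the water load.
- **Aim 2 is restricted to completers.** Its sentence in 9.6 predicts a result and does not define an analysis set. The aims in 9.1 compare ADAPT with waitlist without a completer restriction.
- **Worsening will go unseen in the waitlist.** The waitlist's first scheduled adverse event query is at the post assessment, but 7.3 provides monitoring in all phases and 7.4 records spontaneous reports.
- **The trigger is narrow.** It needs both distress and pain to rise, or a clinical judgement, and the plan expects low risk.

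These points limit the size and remove any claim about direction. They do not settle the conflict between 9.3 and 9.6 or supply a date for early stoppers. ML and MNAR methods help with missing scans, at the price of assumptions that about 20 children per arm cannot test. They do nothing for a child who was scanned but excluded.

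**Conclusion.** The point holds as a gap in the plan. The Aim 1 wording in 9.6 contradicts 9.3 and conditions the ADAPT arm, but not the waitlist, on an event after randomization. Sections 8 and 6.2.5 make outcome-related loss or exclusion possible in ADAPT without a counterpart rule in the waitlist.

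Size and net direction are unknown, because the documents give no arm split, no rate of stopping for worsening and no correlation with the endpoint. The effect ranges from zero, if losses are logistical, to a marked distortion only in an extreme case in which every expected loss is a worst-off ADAPT child. The middle case of 0.05 to 0.11 SD rests wholly on the assumed rho and split. The change is still worth making before post visits take place, since a missed scan cannot be recovered and the remedy is mostly wording.

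**What to change.** 1. **Section 9.6.** Analyse all randomized children as assigned for Aims 1 and 2, using every usable post scan whether or not ADAPT was completed. Handle children without the post-water-load scan by the ML and MNAR methods already named; any pre-water-load series they have can serve as auxiliary data, not as the endpoint. Make a completer analysis secondary, and reword the Aim 2 prediction to match. This set is wider than 9.3, which should be aligned with it.
2. **Section 6.2.5, matched in the Précis and section 3.** At assignment, give every child in both arms a target post-scan date 8 weeks later, with a window of weeks 7 to 12. A child who stops ADAPT early keeps that date, is scanned only with permission and may decline the water load.
3. **Section 8.** Record stopping ADAPT, with date and reason, separately from withdrawing from outcome assessment. Two weeks without contact should end treatment only. Report reasons for missing scans and weeks from assignment to scan, by arm. The clinical stopping criteria stay as they are.

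**Cost.** Wording, one case report form field, earlier booking and a few extra scans, with some burden on children who are doing badly. The effect is diluted: if stopped children gain nothing, 0.40 × (1 − k/25) gives 0.38 SD with 1 of 25 stopped, 0.37 with 2 and 0.32 with 5. Some ADAPT scans may still fall later than most waitlist scans, as they do now; reporting the interval by arm will show it. Where a child declines the water load, the Aim 1 endpoint stays missing.

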## 9. STATISTICAL CONSIDERATIONS

### 9.1 General Design Issues

The statistical hypotheses:

**Aim 1.** Left AMY-PFC functional connectivity will be significantly diminished (i.e., evidence of decreased hyperconnectivity) during the water load symptom provocation task (WL-SPT) post ADAPT vs. waitlist.

**Aim 2.** Brain activations associated with cognitive (PFC), affective (pgACC, AMY), and visceral afferent (INS, thalamus, aMCC, S1 & S2) pain will significantly be more diminished after ADAPT vs. waitlist.

*Exploratory Aim.* Changes in functional connectivity and brain activations following ADAPT will correspond to reductions in pain (intensity and unpleasantness) and anxiety ratings.

The choice of study design (blinded clinical trial) will enable us to answer these research questions.

Primary and secondary outcome measures are obtained from neuroimaging data. The brain regions selected have been shown in prior literature to be related to chronic pain and response to psychological interventions for the management of chronic pain conditions.

## 9.2 Sample Size and Randomization

We've used the following tool (<http://neuropowertools.org/neuropower/neuropowerinput/>) to conduct sample size calculations for the fMRI portion of the study. Power calculations were based on prior studies conducted by the PI's previous study mentor, who collected functional connectivity data 1) pre and post psychological therapy for pediatric pain (migraine), and 2) comparing individuals with pediatric pain (migraine) to healthy controls. While these groups are not synonymous with those proposed in the current study (which aims to compare youth with FAPD who have received psychological therapy for pain and anxiety to those in a waitlist control condition), this preliminary data yields meaningful information by which we can estimate the power required for the proposed investigation. The power calculations and sample size requirements are detailed below:

*For within group changes*, we relied on the pre/post data following a psychological therapy for pediatric pain (migraine). Here we found that a total sample size of 34 would be required for power of .8 and  $p < 0.05$ . *For between group changes*, we utilized data comparing youth with chronic pain (migraine) to healthy controls. Based on these data, a total of 35 subjects are required for power of .8 and  $p < 0.05$ . All comparisons were calculated using z-transformed statistical images of the whole brain, a cluster-forming threshold of  $z > 3.1$  and  $p < 0.05$ , and a Gaussian Random Field theory-based approach for multiple comparisons. For these complex data, statistical power is defined as an 80% probability of correctly detecting an active peak for all peaks above the cluster-forming threshold. We note moderate to large effects observed for within and between group studies; thus, a total sample size of 40 ensures we are adequately powered to observe at least moderate (e.g. mean effect size difference of 0.4 or greater) effects.

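### Section 9.2 claims that 40 participants secure power for an effect of 0.4, but no calculation supports this for ADAPT versus waitlist and the metric of 0.4 is not defined

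*Combined protocol and SAP*

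**What the plan says.** Aim 1 in section 9.1 concerns left AMY-PFC connectivity "during the water load symptom provocation task (WL-SPT) post ADAPT vs. waitlist". Every participant is scanned at baseline, and section 6.2.5 adds that "A post assessment (including fMRI) will be completed for all participants". Section 9.6 plans mixed effects ANOVAs.

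Section 9.2 sizes the trial with a web-based peak-power tool and imaging data from earlier migraine studies. For within-group change, using pre/post therapy data: "Here we found that a total sample size of 34 would be required for power of .8". For between-group differences, using migraine patients against healthy controls: "Based on these data, a total of 35 subjects are required for power of .8". The plan is open that these are proxies: "While these groups are not synonymous with those proposed in the current study". It also defines power in terms of peaks: "statistical power is defined as an 80% probability of correctly detecting an active peak for all peaks above the cluster-forming threshold".

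It then moves to the trial itself. "We note moderate to large effects observed for within and between group studies" is the only link offered before the conclusion that "a total sample size of 40 ensures we are adequately powered to observe at least moderate (e.g. mean effect size difference of 0.4" or greater.

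**The concern.** The last step does not follow. That earlier studies showed moderate to large effects says nothing about the smallest effect that 40 participants can detect in a different comparison. Neither source design is a randomized comparison of therapy with waitlist, and no calculation in the documents contains the value 0.4. The metric is also missing: 0.4 could be a between-arm standardized difference, a difference in change, a within-person effect, Cohen's f or a correlation, and power at 40 differs widely among these.

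This sentence is the plan's only statement of the effect size that 40 participants can detect. A reader who relies on it could take a null primary result as evidence against a moderate effect. The plan discloses that the source groups differ. It does not disclose that power for 0.4 may be well below 80%.

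**Working it through.** **The plan's own figures.** The 34 and 35 cannot be reproduced or refuted, because the input images and their effect sizes are not in the documents. The 40 agrees with the recruitment chain in section 4: 50 at baseline × 0.90 retained = 45, and 45 × 0.90 with usable scans = 40.5, given as 40. It is already the usable-data number, so no further loss is deducted below.

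**Inputs.**
- From the documents: 40 usable participants, effect 0.4, alpha 0.05, target power 0.80, and 17 to 25 per arm.
- Assumed: equal arms (20 each), a two-sided test (sidedness is not stated), one summary connectivity measure, and pre/post correlation r of 0.5 to 0.8. The documents give no r.

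Power is from the noncentral t distribution.

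**1. Between-arm difference at a single visit.** Noncentrality = d × √(n/2) = 0.4 × √10 = 1.265, df = 38, critical t = 2.024.

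| Per arm | Power for 0.4 | Detectable at 80% power |
|---|---|---|
| 17 | 20% | 0.99 SD |
| 20 | 23% | 0.91 SD |
| 25 | 28% | 0.81 SD |

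One-sided power at 20 per arm is 34%. Two-sided 80% power for 0.4 would take about 100 per arm (99.1 before rounding up).

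**2. Group-by-time contrast.** Here 0.4 is the between-arm difference in change, in single-visit SDs. The SD of change is √(2(1 − r)), so the standardized effect is 0.4/√(2(1 − r)), with df = 38 and 20 per arm.

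| r | Standardized effect | Power, two-sided | Power, one-sided | Detectable at 80%, two-sided |
|---|---|---|---|---|
| 0.5 | 0.400 | 23% | 34% | 0.91 SD |
| 0.7 | 0.516 | 36% | 48% | 0.70 SD |
| 0.8 | 0.632 | 50% | 63% | 0.58 SD |
| 0.9 | 0.894 | 79% | 87% | 0.41 SD |

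Two-sided power reaches 80% at r = 0.903. If 0.4 is instead in units of the SD of change, power is 23% whatever r is.

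**3. Readings that come near or above 80%.**
- One-sample pre/post test on all 40: noncentrality = 0.4 × √40 = 2.53; power 69% two-sided, 80% one-sided. This is not the arm comparison, and only about 20 of the 40 receive ADAPT before the post scan. With those 20, two-sided power is 40%.
- Cohen's f = 0.4 for two groups is d = 0.8: 69% two-sided, 80% one-sided.
- A correlation of 0.4 is d = 2 × 0.4/√(1 − 0.16) = 0.87: 77% two-sided.
- Cohen's f = 0.4 for the interaction at r = 0: 94%. Since f = D/(4 SD), this means a difference in change D of 1.6 SD.

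Each of these is either a different contrast or a much larger effect than a between-arm 0.4 SD.

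**The case against.** The strongest defence is that nothing in section 9.2 is shown to be miscalculated. The 34 and 35 come from a recognised type of peak-based calculation, 40 exceeds both, and the plan names its proxies, says that the groups differ and defines power peak by peak. All of this stands. A reader might infer that the 34 and 35 are wrong, that the trial's true power is 23%, or that enrolment must rise. The documents support none of these. The source images are not available, the percentages depend on one reading of 0.4, and the planned seed-to-whole-brain analysis is not a single-measure t-test.

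A second defence is that 0.4 may be another metric, perhaps the one-sample pre/post reading, where 40 gives 80% one-sided. That may be where the figure came from, but it does not bear on ADAPT versus waitlist.

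Third, Aim 1 is directional, so one-sided testing might be intended. Group-by-time power is then 34% to 63% over the assumed correlations, still short of 80%.

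Fourth, adjusting for baseline connectivity would help: 30% to 54% two-sided at r = 0.5 to 0.8 (effect 0.4/√(1 − r²), df = 37). The plan does not state that analysis. The control covariates it names are pubertal status and subjective pain levels, with age optional. The range may be quoted only with that label.

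**Conclusion.** The statement that 40 participants secure power for 0.4 or greater is not supported for the primary contrast, and without a metric it cannot be checked. The fault lies in that sentence, not in the 34 and 35. If 0.4 is a standardized between-arm difference, two-sided power at 20 per arm is about 23% at a single visit and 23% to 50% for the group-by-time contrast. On that reading a true effect of 0.4 would be missed in roughly 50% to 77% of such trials. This rests on equal arms, one summary measure, and correlations of 0.5 to 0.8 that are assumed. A correlation near 0.9 would bring two-sided power to 80%, so the claim is unsupported rather than disproved. It should be corrected, because it governs how a null primary result will be read.

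**What to change.** In section 9.2, delete the claim that 40 ensures power for 0.4 or greater. Replace it with a detectable effect for ADAPT versus waitlist that carries its metric and assumptions, for example:

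> As a single-measure benchmark, not the whole-brain analysis, 20 usable participants per arm at two-sided 0.05 give 80% power for a between-arm difference of about 0.9 SD at a single visit, or about 0.9 / 0.7 / 0.6 SD for a group-by-time contrast at an assumed pre/post correlation of 0.5 / 0.7 / 0.8. Under these assumptions a null result would not exclude a moderate effect.

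If 0.4 was meant in another metric, name it and show the calculation for this contrast. The 34 and 35 can stay, described as peak-wise results for the migraine designs.

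The cost is wording in one section. Enrolment, endpoint and analysis are unchanged; the only downside is a less favourable stated power.
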